2.2 Study Agent

Lenalidomide is an immunomodulatory compound (IMiD) compound, a class of agents that have both immunomodulatory and anti-angiogenic properties. Lenalidomide has been demonstrated to possess anti-angiogenic activity through inhibition of bFGF, VEGF and TNF-alpha induced endothelial cell migration, due at least in part to inhibition of Akt phosphorylation response to bFGF (20). In addition, lenalidomide has a variety of immunomodulatory effects. Lenalidomide stimulates T cell proliferation, and the production of IL-2, IL-10 and IFN-gamma, inhibits IL-1 beta and IL-6 and modulates IL-12 production (25).0 Upregulation of T cell derived IL-2 production is achieved at least in part through increased AP-1 activity (26). 0

Although the exact antitumor mechanism of action of lenalidomide is unknown, a number of mechanisms are postulated to be responsible for lenalidomide's activity. The majority of this information has been derived from studied in multiple myeloma. Lenalidomide increases T cell proliferation, which leads to an increase in IL-2 and IFN-gamma secretion. The increased level of these circulating cytokines augment natural killer cell number and function, and enhance natural killer cell activity to yield an increase in multiple myeloma cell lysis. In addition, lenalidomide has direct activity against multiple myeloma and induces apoptosis or G1growth arrest in multiple myeloma cell lines and in multiple myeloma cells of patients resistant to melphalan, doxorubicin and dexamethasone⁵.

Indications and Usage:

Lenalidomide is indicated for the treatment of patients with transfusion-dependent anemia due to Low- or Intermediate-1-risk myelodysplastic syndromes associated with a deletion 5q cytogenetic abnormality with or without additional cytogenetic abnormalities. Lenalidomide is approved in combination with dexamethasone for the treatment of patients with multiple myeloma. Lenalidomide is also approved in patients with mantle cell lymphoma whose disease has relapsed or progressed after two therapies, one of which included bortezomib **Adverse Events**

The most frequently reported adverse events reported during clinical studies with lenalidomide in oncologic and non-oncologic indications, regardless of presumed relationship to study medication include: anemia, neutropenia, thrombocytopenia and pancytopenia, abdominal pain, nausea, vomiting and diarrhea, dehydration, rash, itching, infections, sepsis, pneumonia, UTI, Upper respiratory infection, atrial fibrillation, congestive heart failure, myocardial infarction, chest pain, weakness, hypotension, hypercalcemia, hyperglycemia, back pain, bone pain, generalized pain, dizziness, mental status changes, syncope, renal failure, dyspnea, pleural effusion, pulmonary embolism, deep vein thrombosis, CVA, convulsions, dizziness, spinal cord compression, syncope, disease progression, death not specified and fractures.

Second New Cancers

[figure not shown]
In clinical studies of newly diagnosed multiple myeloma, a higher number of second cancers were reported in patients treated with lenalidomide as induction therapy and/or bone marrow transplant followed by lenalidomide. This risk seems to be greatest when the duration of lenalidomide therapy exceeded 2 years.

Complete and updated adverse events are available in the Investigational Drug Brochure and the IND Safety Letters.

Lenalidomide Description

Lenalidomide, a thalidomide analogue, is an immunomodulatory agent with anti-angiogenic properties. The chemical name is 3-(4-amino-1-oxo 1,3-dihydro -2*H*-isoindol-2-yl) piperidine-2,6-dione and it has the following chemical structure:

Chemical Structure of Lenalidomide

3-(4-amino-1-oxo 1,3-dihydro-2H-isoindol-2-yl) piperidine-2,6-dione

The empirical formula for lenalidomide is $C_{13}H_{13}N_3O_3$, and the gram molecular weight is 259.3.

Lenalidomide is an off-white to pale-yellow solid powder. It is soluble in organic solvent/water mixtures, and buffered aqueous solvents. Lenalidomide is more soluble in organic solvents and low pH solutions. Solubility was significantly lower in less acidic buffers, ranging from about 0.4 to 0.5 mg/ml. Lenalidomide has an asymmetric carbon atom and can exist as the optically active forms S(-) and R(+), and is produced as a racemic mixture with a net optical rotation of zero.

Clinical Pharmacology

Mechanism of Action:

The mechanism of action of lenalidomide remains to be fully characterized. Lenalidomide possesses immunomodulatory and antiangiogenic properties. Lenalidomide inhibited the secretion of pro-inflammatory cytokines and increased the secretion of anti-inflammatory cytokines from peripheral blood mononuclear cells. Lenalidomide inhibited cell proliferation with varying effectiveness (IC50s) in some but not all cell lines. Of cell lines tested, lenalidomide was effective in inhibiting growth of Namalwa cells (a human B cell lymphoma cell line with a deletion of one chromosome 5) but was much less effective in inhibiting growth

of KG-1 cells (human myeloblastic cell line, also with a deletion of one chromosome 5) and other cell lines without chromosome 5 deletions. Lenalidomide inhibited the expression of cyclooxygenase-2 (COX-2) but not COX-1 in vitro.

Pharmacokinetics and Drug Metabolism

Absorption:

Lenalidomide, in healthy volunteers, is rapidly absorbed following oral administration with maximum plasma concentrations occurring between 0.625 and 1.5 hours post-dose. Co-administration with food does not alter the extent of absorption (AUC) but does reduce the maximal plasma concentration (Cmax) by 36%. The pharmacokinetic disposition of lenalidomide is linear. Cmax and AUC increase proportionately with increases in dose. Multiple dosing at the recommended dose-regimen does not result in drug accumulation.

Pharmacokinetic analyses were performed on 15 multiple myeloma patients treated in the phase I studies. Absorption was found to be rapid on both Day 1 and Day 28 with time to maximum blood levels ranging from 0.7 to 2.0 hours at all dose levels (5mg, 10mg, 25mg, and 50mg). No plasma accumulation was observed with multiple daily dosing. Plasma lenalidomide declined in a monophasic manner with elimination half-life ranging from 2.8 to 6.1 hours on both Day 1 and 28 at all 4 doses. Peak and overall plasma concentrations were dose proportional over the dosing range of 5mg to 50mg. Exposure (AUC) in multiple myeloma patients is 57% higher than in healthy male volunteers.

Pharmacokinetic Parameters

Distribution

In vitro (¹⁴C)-lenalidomide binding to plasma proteins is approximately 30%.

Metabolism and Excretion

The metabolic profile of lenalidomide in humans has not been studied. In healthy volunteers, approximately two-thirds of lenalidomide is eliminated unchanged through urinary excretion. The process exceeds the glomerular filtration rate and therefore is partially or entirely active. Half-life of elimination is approximately 3 hours.

Supplier

Celgene Corporation will supply lenalidomide (Revlimid[®]) to study participants at no charge through Celgene's Revlimid Risk Evaluation and Mitigation Strategy[™] (REMS) (formerly known as RevAssist[®] Program).

[figure not shown]
2.3 Rationale

There have been a number of case reports indicating responses with thalidomide and to a lesser extent lenalidomide in LCH. However, these agents have not been systematically studied and the mechanism of action remains unclear

2.4 Correlative Studies Background

Preclinical data suggest that polymorphisms of the TNF- α promoter occur in LCH patients and that TNF- α levels are elevated in patients with LCH. We will therefore measure baseline TNF- α levels and obtain serial measurements every 2 months for one year or until the patient is removed from protocol (whichever is sooner). This assay will be performed by a reference laboratory (Mayo Clinic).

V600E mutations have been described in up to 50% of patients with ECD and LCH. A commercially available cell free DNA urine assay now exists. In a study of ECD patients with available archival tissue, the result of BRAF mutation analysis was concordant with plasma and urine cfDNA results in all 3 patients (100% agreement, kappa 1.00). In all 6 patients studied on this protocol, BRAF mutation analysis of plasma and urine cfDNA was concordant in 5 of 6 patients (83% agreement, kappa 0.67). We therefore will check baseline urine cell free DNA for BRAF V600E mutations and perform tissue testing for the V600E mutation whenever feasible (either by immunohistochemistry or molecular analysis depending on tissue availability). In addition, we will perform droplet digital PCR assays for BRAF mutations through the blood biomarker lab of the Belfer Institute. The Belfer group has developed a novel assay utilizing droplet digital PCR (ddPCR) technology to perform noninvasive and quantitative genotyping on cfDNA collected from plasma samples. This assay utilizes ddPCR to emulsify collected cfDNA from patient plasma into approximately 20 000 droplets that undergo individualized PCR reactions and analysis allowing for the quantification of mutant versus wildtype copy number [Figure 1]. Previously published work by this group (Oxnard et al, CCR, 2014) has demonstrated the technical feasibility and accuracy of this plasma genotyping assay for detecting BRAF mutations in NSCLC patients. This assay is both highly sensitive and quantitative which creates unique advantages over previous plasma genotyping methods. In addition, the quantitative nature of this assay combined with quality control methods can minimize the false positive results that have plagued earlier assays. The quantitative nature of this assay may also be exploited to allow prediction of early treatment failure as well as the development of treatment resistance.

Patients who have a detectable BRAF V600E mutation in the urine and/or plasma at baseline will have serial measurements every 2 months for 12 months or until protocol discontinuation (whichever occurs sooner). Note, if patients have a positive urine or serum BRAF assay both tests will repeated at all of the aforementioned timepoints. The results of urine and ddPCR-based plasma genotyping will be compared to tissue genotyping for BRAF V600E.

In a descriptive fashion we will investigate whether serum TNF- α levels, ddPCR for BRAF and/or urine cell free DNA harboring the BRAF V600E serves as a biomarker for response.

3. PARTICIPANT SELECTION

Patients aged 18 or older with histologically confirmed Langerhans cell histiocytosis, Erdheim-Chester disease, or histiocytic sarcoma will be eligible. Confirmation of pathology at Brigham and Women's Hospital is preferred but patients may be enrolled based upon outside review of pathology if in the opinion of the principle investigator the pathology is consistent with LCH, ECD, or HS and if a delay in treatment due to review of pathology at BWH would be detrimental to the patient. Tissue will be requested for Oncopanel testing on all patients but this is not an eligibility criteria. Patients will be consented to DFCI protocol 11-104 for Oncopanel testing. Patients who decline participation in this companion protocol will not have material sent for Oncopanel.

Patients with LCH must require systemic treatment according to the Histiocyte Society LCH Evaluation and Treatment Guidelines (2009). There is no limit on the number of prior therapies received so long as the patient otherwise meets eligibility criteria. Patients with HS that cannot be surgically excised and/or encompassed in a radiation field will be eligible even if they have not received prior systemic therapy.

Laboratory tests required for eligibility must be completed within 14 days of registration and radiographic tests must be completed within 30 days of registration.

Since the response criteria differ for histiocyte disorders than for other malignancies, radiographically detectable disease is required but does not need to be bidimensionally measurable as in Cheson criteria.

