3.2 Exclusion Criteria

- 3.2.1 Prior chemotherapy or radiation within 2 weeks (6 weeks for nitrosoureas or mitomycin C) prior to entering the study or those who have not recovered from adverse events due to agents administered more than 2 weeks earlier.
- 3.2.2 Participants who are receiving any other investigational agents.
- 3.2.3 Prior treatment with lenalidomide. Patients previously treated with thalidomide who discontinued treatment for reasons aside from an adverse reaction to thalidomide are permitted.
- 3.2.4 History of another invasive malignancy unless treated with curative intent 5 years or more prior to study entry. Patients with localized carcinoma of the cervix, non-melanoma skin cancer, or early stage prostate cancer requiring observation only are eligible regardless of timing of diagnosis.
- 3.2.5 Uncontrolled intercurrent illness including, but not limited to, ongoing or active infection, symptomatic congestive heart failure, unstable angina pectoris, cardiac arrhythmia, or psychiatric illness/social situations that would limit compliance with study requirements.
- 3.2.6 Pregnant women are excluded from this study because lenalidomide has known teratogenic effects. Because there is an unknown but potential risk for adverse events in nursing infants secondary to treatment of the mother with lenalidomide, breastfeeding should be discontinued if the mother is treated with lenalidomide.
- 3.2.7 Known active hepatitis B (HBV) or hepatitis C (HCV) infection. Patients who are positive only for HBV surface antibody as a result of prior vaccination are eligible. Patients with a positive HBV core antibody but undetectable HBV viral load are eligible.
- 3.2.8 HIV-positive participants on combination antiretroviral therapy are ineligible because of the potential for pharmacokinetic interactions with lenalidomide. In addition, these participants are at increased risk of lethal infections when treated with marrow-suppressive therapy. Appropriate studies will be undertaken in participants receiving combination antiretroviral therapy when indicated.
- 3.2.9 Concomitant corticosteroids unless patient has been on a stable dose of prednisone (or equivalent) of ≤ 10 mg daily for at least 2 weeks prior to first dose of study drug.
- 3.2.10 Inability to swallow pills.

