5. TREATMENT PLAN

Treatment will be administered on an outpatient basis. Expected toxicities and potential risks as well as dose modifications for lenalidomide are described in Section 6 (Expected Toxicities and Dosing Delays/Dose Modification). No investigational or commercial agents or therapies other than those described below may be administered with the intent to treat the participant's malignancy.

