10. STUDY CALENDAR

Baseline evaluations are to be conducted within 1 week prior to start of protocol therapy. Scans and x-rays must be done \leq 4 weeks prior to the start of therapy. In the event that the participant's condition is deteriorating, laboratory evaluations should be repeated within 48 hours prior to initiation of the next cycle of therapy.

Assessments must be performed prior to administration of any study agent. Study assessments and agents should be administered within \pm 3 days of the protocol-specified date, unless otherwise noted.

	Pre- Study	C1 D1	C1 D15	C2 D1	C2 D15	C3 D1	C3 D15	C4 D1	C5 D1	C6 D1	C7 D1	C8 D1	C9 D1	C10 & 11 D1	C12 D1	Off Treatment ^l	Follow Up ^m
Lenalidomide		Х	Х	Х	Х	Х	Х	Х	Х	Х	Х	Х	Х	Х	Х		
Anticoagulation		Х	Х	Х	Х	Х	Х	Х	Х	Х	Х	Х	Х	Х	Х	X ^h	
Informed consent	Х																
Demographics	Х																
Medical history	Х																
Concurrent meds			Х														X
Physical exam	Х	Х	Х	Х		Х		Х		Х		Х	Х		Х	Х	Х
Vital signs ^a	Х	Х	Х	Х		Х		Х		Х		Х	Х		Х	Х	Х
Height	Х	Х	Х	Х		Х		Х		Х		Х	Х		Х		Х
Weight	Х	Х	Х	Х		Х		Х		Х		Х	Х		Х	Х	Х
Performance status	Х	Х		Х		Х		Х		Х		Х	Х		Х	Х	Х
CBC w/diff, plts	Х	$\mathbf{X}^{\mathbf{j}}$	Х	\mathbf{X}^{j}	X^k	Х	X^k	Х		Х		Х	Х		Х	Х	Х
Serum chemistry ^b	Х	Х	Х	Х	X^k	Х	X^k	Х		Х		Х	Х		Х	Х	Х
EKG	Х																
Bone marrow biopsy	\mathbf{X}^{i}																\mathbf{X}^{i}
Adverse event evaluation			Х														X
Tumor measurements ^c	Х					Х				Х			Х		Х	Х	Х
Radiologic evaluation ^d	Х					Х				х			Х		Х	х	Х
B-HCG ^e	X ^b	Х		Х		Х		Х		Х		Х	Х		Х		Х
Urine/ Plasma Assay for BRAF mutation ^f	Xe					Х				х					Х	Х	Х
Serum TNF-alpha ^g	Х					Х				X					Х	Х	Х

a: Temperature, BP, HR and O2 saturation by pulse oximetry at rest.

b: Albumin, alkaline phosphatase, total bilirubin, bicarbonate, BUN, calcium, chloride, creatinine, glucose, potassium, total protein, SGOT [AST], SGPT [ALT], sodium.

c: Tumor measurements are repeated at C3D1, C6D1, C9D1 and C12D1 and then every 3 months thereafter until month 24. After month 24 tumor assessments will occur every 6 months (+/- 2 weeks) until month 36 from treatment initiation. Documentation (preferably radiologic) must be provided for participants removed from study for progressive disease. A window of +/- 1 week is allowed prior to month 24 but tumor assessments must occur prior to dosing on the relevant cycle when active treatment is being administered

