11.1.1 Methods for Evaluation of Disease

All measurements should be taken and recorded in metric notation using a ruler, calipers, or a digital measurement tool. All baseline evaluations should be performed as closely as possible to the beginning of treatment and never more than 4 weeks before the beginning of the treatment.

The same method of assessment and the same technique should be used to characterize each identified and reported lesion at baseline and during follow-up. Imaging-based evaluation is preferred to evaluation by clinical examination unless the lesion(s) being followed cannot be imaged but are assessable by clinical exam.

Clinical lesions. Clinical lesions will only be considered measurable when they are superficial (*e.g.*, skin nodules) and \geq 5 mm in diameter as assessed using calipers. In the case of skin lesions, documentation by color photography, including a ruler to estimate the size of the lesion, is recommended. Skin lesions are considered non-target lesions for response assessment and will be described qualitatively as resolved, improved, stable, or progressive.

PET/CT: this is the preferred method of evaluation for all patients. Because of the propensity of histiocyte disorders to involve the skin and the bones of the skull, the PET/CT should encompass the area from the scalp to the toes. If PET/CT is not covered by insurance, a CT of the chest, abdomen and pelvis in combination with a bone scan is an acceptable alternative.

MRI: MRI is required for all patients at baseline and must be repeated at specified timepoints only if abnormal at baseline or if normal at baseline but there is subsequent clinical suspicion of a CNS recurrence.

11.1.2 Response Criteria

In contrast to lymphoma or other malignancies the terms "remission" or "relapse" should be avoided. In accordance with the nature of LCH the following definitions should be applied to judge the effect of treatment. The response criteria stated below has been designed by the Histiocyte Society to be applied in therapeutic studies of LCH and should be used for therapeutic decisions:

Table 3 Definition of disease state by organ system

NON ACTIVE DISEASE (NAD)	no evidence of disease	resolution of all signs or symptoms
	regressive disease	regression of signs or symptoms, no new lesions
ACTIVE DISEASE (AD)	stable disease	persistence of signs of symptoms, no new lesions

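### The baseline scan can precede the end of prior treatment, so shrinkage from that treatment could count as lenalidomide response

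*Combined protocol and SAP*

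**What the plan says.** **Scan timing.** Section 3 says that "radiographic tests must be completed within 30 days of registration". Two other places tie imaging to the first dose and are tighter in practice. The study calendar (Section 10) limits scans to "4 weeks prior to the start of therapy", and Section 11.1.1 says baseline evaluations are "never more than 4 weeks before the beginning of the treatment". Section 11.1.1 also asks that they be done close to the start of treatment.

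**Prior therapy.** Exclusion 3.2.1 covers "Prior chemotherapy or radiation within 2 weeks (6 weeks for nitrosoureas or mitomycin C) prior to entering the study". Its second limb, on agents given more than 2 weeks earlier, concerns only recovery from their adverse events. Exclusion 3.2.2 keeps out "Participants who are receiving any other investigational agents", with no interval after stopping. Exclusion 3.2.3 says "Patients previously treated with thalidomide who discontinued treatment for reasons aside from an adverse reaction to thalidomide are permitted", again with no interval. Section 3 sets no limit on the number of prior therapies. Section 2.1 describes BRAF inhibitors and thalidomide as active in these diseases, and interferon as common front-line treatment for ECD.

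**During the study.** Section 5 states that "No investigational or commercial agents or therapies other than those described below may be administered" to treat the malignancy.

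**Response and decision rule.** Under Section 13.5 a responder is a patient whose best overall response on study therapy is complete resolution or regression. Section 11.1.2.3 asks for responses to last 8 weeks. Section 13.1 sets 12 patients, a threshold of 3 responses and an unworthy rate of 5%.

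**The concern.** No passage requires the baseline response scan to follow the last dose or fraction of earlier treatment. The scan window (4 weeks) is longer than the treatment-free period (2 weeks), so a compliant patient can still be receiving other therapy after the scan that later serves as the reference for response. Shrinkage from that therapy then looks like lenalidomide response. No rule in Section 11 sets aside irradiated lesions.

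The trial has no control arm that would show such an effect, and its conclusion turns on 3 responses. According to Section 13.1, the result will decide whether a larger phase II trial is warranted.

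**Working it through.** **1. Overlap in days.** Count days from the first dose.
- Earliest permitted baseline scan: day -28 (Sections 10 and 11.1.1).
- Latest permitted end of chemotherapy or radiation: 14 days before entry (3.2.1). I take entry to mean registration. If the first dose comes g days after registration, this is day -(14 + g).
- Largest overlap: 28 - (14 + g) = 14 - g days. It is 14 days when registration and first dose coincide.
- Nitrosoureas and mitomycin C: their 6-week period is 42 days, which exceeds 28, so there is no overlap.
- An agent outside 3.2.1 on a literal reading has no stated interval, so the overlap could be nearly the whole 28 days.

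**2. The plan's own figures.** Exact (Clopper-Pearson) 90% limits for 3/12 are 7.2% to 52.7%, matching the stated 7-53%. For 2/12 they are 3.0% to 43.8%, which include 5%, so the stated cut-off also reproduces.

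**3. Chance of meeting the threshold when the true rate is 5%.** With k certain carry-over responders, the other 12 - k patients must supply 3 - k responses: P(X ≥ 3 - k), with X ~ Bin(12 - k, 0.05).

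| k | Calculation | Probability |
|---|---|---|
| 0 | P(at least 3 of 12) | 0.0196 |
| 1 | P(at least 2 of 11) = 1 - 0.95^11 - 11(0.05)(0.95^10) | 0.102 |
| 2 | P(at least 1 of 10) = 1 - 0.95^10 | 0.401 |

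**4. Carry-over that is possible but not certain.** Suppose m of the 12 were recently treated and each has carry-over probability q. Each of them then counts as a responder with probability 1 - 0.95(1 - q), and the others with probability 0.05. The exact chance of at least 3 responses is:

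| m | q | Per-patient probability | Chance of at least 3 |
|---|---|---|---|
| 2 | 0.10 | 0.145 | 3.8% |
| 3 | 0.25 | 0.2875 | 12.3% |
| 4 | 0.25 | 0.2875 | 18.5% |
| 6 | 0.50 | 0.525 | 76.0% |

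The documents give neither m nor q. Both are assumptions, and the table shows only how sensitive the rule is.

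**The case against.** Several parts of the plan work against a false response.

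- **Maintenance.** Scans fall at cycle 3 day 1 and cycle 6 day 1, about 8 and 20 weeks after the first dose. A carry-over effect seen at the first would normally have to persist to the second, with the earlier drug stopped, to meet the 8-week rule.
- **Size and review.** A partial response by the nodal criteria needs a fall of at least 50% in the summed products of the dominant masses and no new sites. Imaging is reviewed centrally.
- **Population.** The objectives specify relapsed/refractory LCH and ECD, and LCH patients must need systemic treatment. A patient shrinking well on earlier therapy would not ordinarily enter. HS patients may have had no systemic therapy at all.
- **Worst case.** The 14 days need the oldest permitted scan, the latest permitted stop and no gap between registration and first dose.
- **Pilot status.** Section 13.1 openly accepts that the response rate may be overestimated.

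The first four points stand as reasons why the risk is lower than the dates alone suggest. They do not close the gap. Later scans are compared with the same early baseline, so a lesion that shrank after irradiation and stayed small passes the 8-week rule. Section 3.1 does not require progression after the last therapy, and criterion 3.1.3 sets no need-for-treatment condition for ECD. Section 2.1 itself gives reasons to stop an active drug without progression: skin toxicity with BRAF inhibitors and the six-month limit on cladribine. The bar in Section 5 applies to protocol treatment and does not cover the days between scan and first dose. The last point concerns imprecision from a small sample, whereas misattributed response is bias in one direction.

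**Conclusion.** The gap is real and worth closing, but it is limited. A patient can comply fully and still receive up to 14 days of chemotherapy or radiation after the baseline scan, possibly longer for agents that 3.2.1 does not clearly cover. How often this would create a false responder cannot be known from the documents. With a threshold of 3 in 12, one or two such patients are enough to change the reading of the trial.

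A reader might infer four stronger things that the documents do not support:
- *That the overlap is 16 days, from 30 minus 14.* The 4-week cap before first dose also applies and is the tighter limit when registration and first dose coincide.
- *That 3.2.1 definitely leaves out BRAF inhibitors, interferon and thalidomide.* The word chemotherapy is undefined, so this is an ambiguity. For thalidomide, 3.2.3 at least requires that it has been stopped.
- *That the false-positive rate is 10.2% or 40.1%.* Those figures assume one or two certain carry-over responders. A milder assumption gives 3.8%, against 2.0% with none.
- *That any shrinkage from earlier treatment would count.* It must reach the response criteria and last 8 weeks.

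**What to change.** 1. Require the baseline response scan to be taken after the last dose or fraction of any prior disease-directed therapy, within the existing 4-week window.
2. State in Section 11 that irradiated lesions do not count toward response unless they progressed after irradiation.
3. State which agents 3.2.1 covers and reconcile it with 3.2.3. Whether any class needs a treatment-free interval, and how long, is for the clinical team.
4. Record the last prior agent and its stop date. Prespecify a sensitivity analysis, with the denominator unchanged, that treats responders whose prior therapy ended after the baseline scan as non-responders.

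**Cost.** For chemotherapy and radiation the 2-week period already leaves room for the scan, so treatment need not be delayed. For other agents there may be an occasional short delay or repeat scan. That is not trivial where PET/CT coverage is uncertain or the disease is aggressive, as in HS.

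**Limit.** This removes the effect of treatment given after the scan. Delayed effects of treatment given before it would remain.
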